8.0 Participant Withdrawal

While participants are encouraged to complete all study evaluations, they may withdraw from the study at any time and for any reason irrespective of the reason, or at the Investigator's decision. Participants who have been withdrawn from the study cannot be re-included in the study. Their inclusion and treatment number must not be re-used.

Participation is voluntary, and refusal to participate will involve no penalty, or loss of benefits to which the participant is otherwise entitled. The participant will be encouraged to maintain contact with the investigator and report any serious adverse events experienced for the 6 months study period. Follow-up following the study period is described in Section 7.9.

An **evaluable** participant will be any participant who receives at least one dose of test material and has at least one post dose assessment.

Screen failures will include any participant who consented and entered into the screening process appropriately, but subsequently did not meet the entry criteria and was not administered study drug. Participants who fail screening will not be followed for safety or activity of study drug, and no other study procedures will be performed.

Those participants who do not complete the study for any reason will be considered a premature termination. (eg. Adverse Event and/or lack of therapeutic effect and/or participants desire to discontinue study procedures/testing but allows for safety follow-up). The procedures for the Visit 7 should be completed when a participant discontinues the study.

- **Adverse Events:** Subjects with adverse events, severe enough to necessitate discontinuation of study drug administration as judged by the investigator. The treating physician should take appropriate clinical action. The condition should be treated according to routines of the clinic. The participant should be followed up regarding the safety measurements stated in the protocol.
- **Consent Withdrawn:** participant decided to withdraw his consent to participate in the study for any reason. In this event the participant refuses to participate in any additional evaluations and is withdrawing their consent for the site to utilize their data going forward. In this event the participant's data post the consent withdrawn will not be utilized in the clinical trial summary in accordance with enactment of 1996 (HIPAA) and subsequent Privacy Rule, required as of April 14, 2003.
- **Lost to Follow-up:** participant failed to return for required visits and cannot be contacted. Reasonable effort should be made by the investigator to contact any

participant who fails to return to the clinic for a scheduled visit in order to complete assessments and retrieve any outstanding data or supplies of study medication. All such efforts should be documented in the source notes. Up to three participants “lost to Follow-up” can be replaced in each dosage cohort for participants that received gene transfer but failed to complete the Visit 4 (week 4) evaluations.

- **Sponsor/Investigator Decision:** A participant may be withdrawn at any time at the discretion of the Sponsor/investigator.
- **Lack of Therapeutic Effect:** A participant may choose to withdraw at any time if they feel that they want to pursue alternative treatment for their ED based on their perceived lack of therapeutic effect.

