3.0 Study Design

This study is double-blind, placebo controlled parallel design Phase 2A trial evaluating the potential activity and safety of two different doses of *h*Maxi-K (16000 µg, and 8000 µg) given in a single administration relative to placebo injected into the corpus cavernosum of the penis.

The proposed study period is approximately 6 months following the single injection of study drug

per participant. This study will enroll 11 participants at *h*Maxi-K doses of 8000 µg, 11 participants at *h*Maxi-K doses of 16000 µg and 13 on placebo. A maximum of 35 participants will be enrolled.

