5.1.1 Packaging and Labeling

Each assigned vial will have a double blinded 2 part detachable label (tear off part to be placed in the participant's source documents). Each vial label will contain the following information:

- Study ION 04-ED
- Participant identification number
- INSTRUCTIONS: Inject contents of both vials into corpora cavernosa
- Store at controlled room temperature once constituted: [REDACTED] C to [REDACTED] C [REDACTED] F to [REDACTED] F).
- CAUTION: New Drug – Limited to investigational use
- Manufactured for Ion Channel Innovations, LLC by Althea Technologies, Inc., San Diego, CA 92121

Note: In each dosing arm, 11 participants will receive *h*Maxi-K and 13 will receive PBS-20% sucrose (placebo).

Sharp Clinical Services, Inc. will prepare 40 kits of product using randomization schedule generated by a Statistical Group. The kits will be shipped to the central pharmacy at Dasman and stored at -20C. Following notification by the site that an eligible participant is to be given the study medication the pharmacy will send the blinded kit to the investigator for use.

The individual participants' double blind patient drug kit will contain a two-part (tear-off) label. The duplicate portion of this label will be detached and affixed to a label page (to be retrieved at study close out by Ion Channel Innovations designated monitor) at the time of randomization and test drug administration. There will be central randomization. The site will be instructed to call the Sponsor or designee for the assigned subject number after each participant's screening visit allowing ample time prior to Visit 2 for shipment of the drug.

The duplicate label from each patient drug kit will be affixed to a separate log in the source documents at Visit 2.

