10.3 Analysis of Endpoints

The methods described in this section will be updated during the course of the study. The final version of the statistical analysis plan (SAP) will be issued before the treatment code is broken.

This double blind, phase 2A study is designed to evaluate the safety and efficacy of a single injection of *h*Maxi-K (8000 and 16000 µg) compared to placebo in individual participants. Both the safety data and data to assess efficacy will be analyzed using summary descriptive statistics for the two cohorts and the total study population. Associations between study therapy and the outcomes will be assessed using-repeated measures analyses, and explored in multivariate models, as needed.

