## 5. Analysis Sets

- **Randomized population:** This will include all the subjects who have been randomized to either of the treatment groups.
- **ITT population:** This will include all the subjects who have been randomized to either of the treatment groups and who have received at least one dose of study treatment.
- **Modified ITT population (Mod-ITT population):** This population will include all subjects in the ITT population who have at least one post dose efficacy assessment.
- **Per Protocol Population (PP Population):** This will include all subjects in the ITT population who report no protocol violations.
- **Safety Population:** This will include all subjects who were randomized to either of the treatment groups and who have received at least one dose of study treatment.

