## **9.2. Descriptive Methods**

The study comprises of two cohorts comprising of three treatment groups namely

- **Cohort 1:** *h*Maxi-K- comprising of two treatment groups; *h*Maxi-K 8000 $\mu$ g and *h*Maxi-K 16000 $\mu$ g
- **Cohort 2:** Placebo- which was administration of PBS-20% sucrose

All outputs will be presented with respect to the above two cohorts and overall. Cohort 1 will be further sub-categorized with respect to the two treatments.

The various baseline and demographic characteristics will be analyzed for the randomized population. For quantitative variables, the following descriptive statistics will be computed: number of subjects (n), number of missing values/subjects, mean, standard deviation, minimum, maximum, median, Q1 and Q3. For qualitative variables, the frequency and percentage of subjects and/or events will be calculated. All listings will include the subject identifiers, the treatment group/cohort that the subject is randomized to and the tables will be presented by the treatment cohorts to which subjects are randomized. The characteristics that will be analyzed are as follows

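### The rule for replacing men lost before Visit 4 cannot be applied without the treatment code, and neither document says how a replacement is allocated

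*Protocol*

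**What the plan says.** The rule is in the Lost to Follow-up bullet of Protocol 8.0. It sets a limit of three men and counts it by treatment: those who have stopped returning and are out of reach "can be replaced in each dosage cohort for participants that received gene transfer but failed to complete the Visit 4 (week 4) evaluations". The same section forbids re-using the number of a withdrawn man, so each replacement needs a new number and a new kit.

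The setting is as follows:

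- **Blinding.** Protocol 3.0: "This study is double-blind, placebo controlled parallel design Phase 2A trial". Under Protocol 10.3 the final SAP "will be issued before the treatment code is broken". No earlier code break is described for replacement.
- **Allocation.** Protocol 5.1.1: "There will be central randomization". The site telephones the sponsor or its designee for a subject number. Forty kits are made up from the randomisation schedule; how the kits beyond 35 divide among the arms is not stated.
- **Size.** Protocol 3.0 and SAP 3 plan 11, 11 and 13 men and cap enrolment at 35.
- **SAP.** It does not mention replacement.

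**The concern.** A replacement rule in a blinded trial should run on information that everyone blinded already has: was the man dosed, and did he come back? This rule adds two conditions that only the code can answer, namely whether he received gene transfer and how many of his dosage cohort have already been replaced. Someone must therefore look up his arm, and the protocol does not say who, or how the answer is kept from the site and from the staff who issue numbers.

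Two things are at stake. The first is the blind. The lost man's arm matters little for his own data, because he has gone. But if his replacement has to join the same arm, that man's treatment may be known before he is dosed, and he then supplies self-reported IIEF and SEP scores at a single site. The second is the randomised comparison. On the literal wording early losses are made good on hMaxi-K and not on placebo, and the way the extra men are allocated is left open.

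**Working it through.** **1. The plan's own figures (background).** Table 2 of Protocol 10.3.2 gives means of 10.0 and 6.6 (difference 3.4), SD 2.5 and alpha 0.0167; tests are one-tailed. Power comes from the noncentral t distribution, with noncentrality 3.4 / (2.5 × √(1/n1 + 1/n2)).

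- 11 v 13: 3.4 / (2.5 × 0.4097) = 3.32 on 22 df, power 84.6%.
- 11 v 11: 3.4 / (2.5 × 0.4264) = 3.19 on 20 df, power 81.0%.
- Attrition: 35 / 0.9 = 38.9, so 39, against the plan's figure of about 40.

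The sample size reproduces and is not in dispute.

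**2. What a replacement discloses, read literally.** Before the rule is used, a dosed man is on hMaxi-K with probability (11 + 11)/35 = 22/35 = 63%. Once he is replaced under a rule limited to gene-transfer recipients, the probability is 100%.

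**3. Does the rule fit the protocol's limits?** A replacement is a new enrolment with a new kit.

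| Reading of the limit | Extra men | Total | Cap 35 | Kits 40 |
|---|---|---|---|---|
| Three per hMaxi-K dose (literal) | 2 × 3 = 6 | 41 | exceeded by 6 | exceeded by 1 |
| Three per arm, placebo included | 3 × 3 = 9 | 44 | exceeded by 9 | exceeded by 4 |

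Once 35 men are enrolled, even one replacement makes 36 and breaches the cap, unless replaced men are not counted towards it. The protocol does not say.

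**4. How often would it be used?** Protocol 10.3.2 expects 10% attrition over 24 weeks: 0.10 × 11 = 1.1 men per dose, 2.2 over both doses. The share lost by Week 4 is not given. Two assumptions bound it, both counting all attrition as loss to follow-up:

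- Constant loss rate: 1 − 0.9^(4/24) = 1.74% by Week 4, so 22 × 0.0174 = 0.38 men on hMaxi-K.
- All loss before Week 4: 2.2 men.

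**5. What does replacement buy?** Suppose 10% are lost and contribute nothing (11 becomes about 10, 13 about 12). One-sided power is then:

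| Comparison | No replacement | hMaxi-K losses replaced |
|---|---|---|
| Dose v placebo | 10 v 12: 80.7% | 11 v 12: 83.0% |
| Dose v dose | 10 v 10: 76.4% | 11 v 11: 81.0% |

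This overstates the gain, because only men lost before Visit 4 can be replaced, and a man seen at Week 1 still contributes data.

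**The case against.** **The wording may be loose.** The protocol sometimes uses active-drug terms for the study injection in general. A dose-limiting toxicity criterion in Protocol 5.2.1, which has to be judged blind, is timed from gene transfer, and the Synopsis speaks of three cohorts, so placebo can be one. On that view the rule covers any dosed man. This is a fair reading, and it makes the exclusion of placebo conditional. Against it, Protocol 1.4 describes hMaxi-K as a gene transfer product and Protocol 5.2 sets the gene product against PBS-sucrose. It also does not rescue the rule, because a limit counted per dosage cohort still cannot be kept without the arms.

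**Disclosure is narrow.** The lost man gives no further data, other men's codes are untouched, and because replacement is optional, not replacing someone tells the site nothing. The sponsor's designee could also apply the rule out of the site's sight. All of this stands as a limit on the harm. The last part is a possibility, not a procedure in the protocol.

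**Stronger readings that the documents do not support.**

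- *Replacements are placed outside randomisation.* Neither document says so. Central randomisation, kits drawn from the schedule and the ban on re-using numbers are all compatible with a scheduled allocation. What can be said is that the mechanism is missing.
- *The hMaxi-K arms could reach 14 and 14, with 6 of 28 men (21%) non-randomised.* That makes 14 + 14 + 13 = 41 men, beyond both the cap and the kits, and the label non-randomised rests on the unsupported reading above.
- *The rule contradicts the analysis sets.* It does not. Protocol 8.0 says that an evaluable "participant will be any participant who receives at least one dose of test material and has at least one post dose assessment", and SAP 5 says of the modified ITT set: "This population will include all subjects in the ITT population who have at least one post dose efficacy assessment". Those passages decide who is analysed; the replacement rule decides who is recruited. A man seen at Week 1 and then lost can be replaced and still be analysed.
- *The limit might be three over both doses.* SAP 9.2 says "The study comprises of two cohorts comprising of three treatment groups namely" and puts both doses in its first cohort, but that grouping is for presenting output, and the protocol's wording points to a count for each dose.

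**Conclusion.** The point holds in a limited form. As written, the rule depends on allocation, has no blinded procedure, does not say how the replacement is allocated, and at its literal maximum (41 men) cannot be carried out within the protocol's own cap of 35 and 40 kits. The need for the code is present on either reading of the gene-transfer phrase; the 63% to 100% disclosure and the exclusion of placebo losses rest on the literal one. Whether a replacement's own arm is revealed depends on whether he must join the lost man's arm, which is not stated.

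The numerical effect is probably small: between about 0.4 and 2.2 men on hMaxi-K would qualify, under the assumptions shown. A reader might infer that the rule unblinds the trial as a whole. It does not; it exposes the lost man and possibly his successor. It should be fixed because it puts the blind and the randomised comparison at avoidable risk for a modest gain in power.

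**What to change.** Amend the Lost to Follow-up bullet of Protocol 8.0 in one of two ways.

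1. **Delete replacement.** Under the assumptions above, power against placebo stays near 81%; dose v dose falls to about 76%.
2. **Make it arm-blind.** Any dosed man lost before Visit 4, whatever his arm, may be replaced up to one overall number. The decision uses blinded follow-up status only, and the new man takes the next unused place on the central schedule. Remove both the gene-transfer condition and the per-cohort count.

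Under option 2, reconcile the number with the other limits. With 40 kits it cannot exceed 40 − 35 = 5, and Protocol 3.0 and SAP 3 must say whether the cap of 35 includes replaced men or is raised. SAP 5 needs no change for this point, since its sets already determine where a replaced man is analysed.

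The cost is one protocol sentence and, under option 2, the matching cap statement. Final arm sizes may differ from 11, 11 and 13 by one or two men.

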9.0 Adverse Events Definitions and Monitoring

9.1 Adverse Event

An adverse event is any unfavorable and unintended diagnosis, symptom, sign (including an abnormal laboratory finding), syndrome or disease which either occurs during the study, having been absent at baseline, or, if present at baseline, appears to worsen.

A treatment emergent adverse event (TEAE) will be considered an event that is temporally associated with the use of the study drug, whether or not considered related to the study drug.

Examples of AEs are as follows:

- Changes in the general condition of the participant
- Subjective symptoms offered by or elicited from the participant
- Objective signs observed by the Investigator or other study personnel
- All concurrent diseases that occur after the start of the study, including any change in severity or frequency of preexisting disease
- All clinically relevant abnormalities in laboratory values or clinically relevant physical findings that occur during the study.

9.2 Serious Adverse Event

A serious adverse event (experience) is defined (21 CFR 312.32) as any adverse experience that suggests a significant hazard, contraindication, side effect or untoward medical occurrence that:

- Results in death,
- Is life threatening,

Note: The term "life-threatening" in the definition of "serious" refers to an event in which the participant was at risk of death at the time of the event; it does not refer to an event which hypothetically might have caused death if it were more severe.

- Requires (or prolongs) hospitalization,
- Causes persistent or significant disability/incapacity,

- Results in congenital anomalies or birth defects, or
- Other conditions which in the judgment of the investigators represent significant hazards.

Medical and scientific judgment should be exercised in deciding whether expedited reporting is appropriate in other situations, such as important medical events that may not be immediately life-threatening or result in death or hospitalization but may jeopardize the participant or may require intervention to prevent one of the other outcomes listed in the definition above.

These should also usually be considered serious.

Note: Examples of such events are intensive treatment in an emergency room or at home for allergic bronchospasm, blood dyscrasias, convulsions or asymptomatic ALT increase > 10 ULN that do not result in hospitalization, or development of drug dependency or drug abuse.

9.3 Assessment of Causality

The relatedness of an adverse event to the study drug is the best estimate of the principal investigator at the time of reporting of the causal relationship between an experimental intervention and an adverse event.

The following study drug relationships will be used for this clinical trial:

Unrelated: There is no temporal relationship between the event and the administration of the study drug or the event is clearly due to the patient's medical condition, other therapies or accident.

Possibly Related: There is some temporal relationship between the event and the administration of the study drug and the event is unlikely to be explained by the patient's medical condition or other therapies.

Probably Related: The temporal relationship between the event and the administration of the study drug is compelling, and the patient's medical condition or other therapies cannot explain the event.

Certainly Related: The event follows a reasonable temporal sequence from administration of the medication or follows a known or suspected response pattern to the medication.

The categories of "Certainly", "Probably" and "Possibly Related" are considered study drug related.

9.4 Severity of Adverse Event

Adverse events included in the toxicity table ([Appendix A](#)) will be graded according to the definitions provided. For adverse events not listed in the toxicity table, assignment of grade based on intensity of symptoms, degree of limitation of usual daily activities, or level of abnormality of objective clinical signs or laboratory parameters will be according to severity using the following criteria:

- Grade 1: transient or minimal symptoms; not interfering in function or ability to perform activity of daily living or require a medication change. No medical intervention required.
- Grade 2: symptoms interfering in function but not with activities of daily living. Minimal or no medical intervention required.
- Grade 3: incapacitating symptoms that interfere with function and activities of daily

living; required bed rest and/or resulted in loss of work or cancellation of social activities. Medical intervention required. Hospitalization possible.

- Grade 4: Considered potentially life threatening (see definition under section 9.2)

A serious adverse event (SAE) requires medical intervention to prevent permanent impairment or death, permanently disability: (bed-ridden or disabling AE), required significant medical intervention/therapy, hospitalization or hospice care or in the judgment of the investigator was a medically significant event. Serious adverse events may be mild, moderate or severe in intensity (e.g., mild stroke).

9.5 Monitoring of Adverse events

The investigator(s) will monitor their participants for the occurrence of adverse events during the course of the study and record all observed adverse events in the case report form.

Adverse Events regardless of seriousness or relationship to study drug, including those

occurring during the Screening period (where applicable), are to be recorded in the CRF. Whenever possible, symptoms should be grouped as a single syndrome or diagnosis. The Investigator should specify the date of onset, maximal intensity, corrective therapy given, outcome, and his/her opinion as to whether there is a reasonable possibility that the Adverse Event was caused by the study drug.

Any adverse events that meet the 4 criteria under Stopping Rules (Section 5.2.1) must be communicated to the sponsor (or designee) within 24 hours of first knowledge of such event

The investigator must provide the sponsor appropriate information concerning any findings suggesting significant hazards, contraindications, side effects or precautions pertinent to the safety of the study drug. The investigator will instruct participants prior to administration of study drug to report any physical changes or new symptoms that they notice during the course of the study. The investigator must report all serious adverse events (defined above) within 24 hours of their onset to Ion Channel Innovations, LLC.:

[REDACTED] M.D.

[name]

[name]

[contact]

[contact]

In case of prolongation of $QT_cF \geq 500$ ms, or an increase in $QT_cF \geq 60$ ms from baseline, a blood sample should be drawn for measurement of serum potassium, calcium, magnesium, and *hSlo* cDNA.

A cardiologist should be consulted, and the participant should continue to have his ECG monitored until the ECG abnormality resolves or becomes stable.

